### 7.6.4. PEP Medications While At Risk of HIV Infection During the Study

Post-exposure prophylaxis (PEP) is defined as treatment with any non-study drug ARV agent other than F/TDF (or generic F/TDF), cabotegravir or HIV vaccine while subjects are at risk of HIV infection as defined in Section 6.2.3.

The number of subjects with any PEP use and the number of PEP uses per subject while at risk of HIV infection during the DB phase, while on-treatment and while off-treatment and at risk of HIV infection will be summarized for the FAS.

The number of PEP uses per subject will be based on unique PEP medication start dates within each subject. Multiple ARV medications with overlapping start and end dates will be counted as only one PEP use. Consecutive PEP medications where the complete medication end date of one PEP medication differs from the complete medication start date of another PEP medication by one day or less will be counted as only one PEP use.

For PEP uses while at risk of HIV infection during the DB phase, if the start or stop date of the ARV medication is incomplete, the month and year (or year alone, if month is not recorded) of the start or stop date will be used to determine whether the ARVs occurred during the at risk of HIV infection period or not. The medication occurred during the at risk of HIV infection period if the month and year of the start or stop (or year of the start or stop, if month is not recorded) of the medication does not meet either of the following criteria:

- The month and year of start of the medication is after the date of the end of the at risk of HIV infection period
- The month and year of stop of the medication is on or before the date of the first dose of study drug

If the start and stop date of ARV medications are complete, the start date is not after the date of the end of the at risk of HIV infection period and the stop date is not on or before first dose date, or the ARV medications are marked as ongoing and start date is on or before the date of the end of the at risk of HIV infection period, the non-ARV medications are considered as occurring during the at risk of HIV infection period. Medications with completely missing start and end dates will not be considered as occurring while at risk of HIV infection during the study.

PEP uses while on-treatment at risk of HIV infection are defined similar to the above PEP uses while at risk of HIV infection, but replacing the date of the end of the at risk of HIV infection period with the minimum of the last dose date and end of the at risk of HIV infection period for subjects that have permanently discontinued study drug. For subjects that have not permanently discontinued study drug, PEP uses are defined as above for PEP uses while at risk of HIV infection.

For PEP uses while off study drug for PrEP (off-treatment) at risk of HIV infection are defined similar to the above PEP uses while at risk of HIV infection, but replacing the first dose date with the last dose date for subjects that have permanently discontinued study drug. Subjects that have not permanently discontinued study drug or subjects that permanently discontinued study drug, but whose end of at risk of HIV infection period is on or before the last dose date will be excluded.

The denominator for subjects with any PEP use or on-treatment PEP use while at risk of HIV infection during the study will be the FAS. The denominator for subjects with off-treatment PEP use while at risk of HIV infection during the study will be subjects in the FAS who have permanently discontinued study drug and have at least one post-last dose HIV laboratory assessment (from either local or Covance laboratory).

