- Latent and Active Reservoir assessment (24 weeks and 48 weeks after HIV infection, and every 48 weeks thereafter)
- T cell response and phenotype (24 weeks and 48 weeks after HIV infection, and every 48 weeks thereafter)
- Viral Sequence Diversity assessment (**24 weeks after HIV infection only**)

— Inflammatory/immune activation biomarkers (**only for participants who acquire HIV**. Done at the first study visit upon confirmation of HIV infection, at 24 weeks and 48 weeks after HIV infection, and every 48 weeks thereafter)

- CASI for sexual risk events and adherence since the last visit
- Collect and review used and unused blinded study drug for accountability and calculate compliance (**not done for participants who have permanently discontinued study drug**)

- OL drug dispensation (**not done for participants who acquire HIV**). If the participant has already taken a dose of blinded study drug on the day of the end of blinded treatment phase visit, they should not begin dosing with OL F/TAF until the next day. If the participant has not taken a dose of blinded study drug on the day of the visit, they should take their first dose of OL F/TAF on the same day of the end of blinded treatment phase visit.
- Adherence and risk reduction counseling including provision of condoms. Participants will be educated on the signs and symptoms of acute HIV-1 infection and will be instructed to call and/or present to the site for evaluation and HIV-1 testing if they develop such symptoms. (**Adherence and risk reduction counseling not done for participants who acquire HIV.**)

█ [REDACTED]

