## 3. GENERAL CONSIDERATIONS FOR DATA ANALYSES

The end of blinded treatment phase analysis will include all data collected from the randomized and the open-label extension (OLE) phase of the study. Only data collected in the double-blinded (DB) phase (ie, DB phase data) will be summarized, if not specified otherwise. Data collected from both phases will be included in data listings.

A subject is considered to have enrolled in the open-label extension if the entry of OLENTRY form is 'yes'. The cutoff date of the OLE phase will be the date of first dose date of the OLE phase if it is available. If the subject is never dosed in the OLE phase, all available data are considered as the DB phase data.

For subjects who are not enrolled in the OLE phase, all available data are considered as the DB phase data. For subjects who are treated in the OLE phase, data collected up to the cutoff date will be considered as DB phase data, and data collected after the cutoff date will be considered as OLE phase data, except for adverse events (AEs), concomitant medications, and death. For AEs, concomitant medications, and death, data collected prior to the cutoff date are considered as DB phase data, and data collected on or after the cutoff date is considered OLE phase data.

Analysis results will be presented using descriptive statistics. In general for categorical (or ordinal) variables, the number and percentage of subjects in each category will be presented; for continuous variables, the number of subjects (n), mean, standard deviation (SD) or standard error (SE), median, first quartile (Q1), third quartile (Q3), minimum, and maximum will be presented.

All statistical tests will be 2-sided and performed at the 5% significance level unless otherwise specified.

By-subject listings will be presented for all subjects in the All Randomized Analysis Set and sorted by subject ID number, visit date, and time (if applicable), unless otherwise specified. Data collected on log forms, such as AEs, will be presented in chronological order within a subject. The treatment group to which subjects were randomized will be used in the listings. Age, MSM/TGW status, race, first dose date and HIV infection date will be included in the listings, as space permits.

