In general, permanent discontinuation of study drug refers to premature discontinuation of study drug or completion of study drug and regardless of any gaps in continuous dosing (ie, temporary discontinuation due to adverse event (AE) or subject request after which subjects may resume study drug).

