### 6.2.3. Definition of Duration of At Risk of HIV Infection in Study

Duration of at risk of HIV infection is defined as the time between Day 1 (first dose date) and the end date (end date Day 1 date +1), where end date is defined as the last at-risk of HIV infection date:

- 1) For subjects who have been diagnosed as infected with HIV during the DB phase: the date of HIV infection diagnosis (as defined in Section 6.2.2)
- 2) For subjects who have not been infected with HIV during the DB phase: the date of the last post-baseline HIV laboratory test (either local HIV or Covance HIV laboratory tests) during the DB phase (may include the 30-day follow-up visit).

Duration of time at risk of HIV infection in study will be summarized using descriptive statistics (n, mean, SD, median, Q1, Q3, minimum, maximum and total person-years) and as the number and percentage of subjects at risk of HIV infection in study for specified periods, ie,  $\geq$  4 weeks (28 days),  $\geq$  8 weeks (56 days),  $\geq$  12 weeks (84 days),  $\geq$  24 weeks (168 days),  $\geq$  36 weeks (252 days),  $\geq$  48 weeks (336 days),  $\geq$  60 weeks (420 days),  $\geq$  72 weeks (504 days),  $\geq$  84 weeks (588 days),  $\geq$  96 weeks (672 days),  $\geq$  108 weeks (756 days),  $\geq$  120 weeks (840 days),  $\geq$  132 weeks (924 days),  $\geq$  144 weeks (840 days), etc.

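### The off-treatment PEP denominator in SAP 7.6.4 admits completers who went straight onto open-label F/TAF, if their last blinded dose is recorded as the day before the exit visit

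*SAP*

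**What the plan says.** SAP 7.6.4 summarises PEP use in three ways: while at risk in the blinded phase, while on treatment, and while off treatment but still at risk. The off-treatment denominator "will be subjects in the FAS who have permanently discontinued study drug and have at least one post-last dose HIV laboratory assessment". The section's only timing exclusion is for participants "whose end of at risk of HIV infection period is on or before the last dose date will be excluded". It sets no minimum off-drug interval and does not mention the first open-label dose.

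Four other rules decide who meets those conditions:

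- **Who has discontinued.** In SAP section 3, "permanent discontinuation of study drug refers to premature discontinuation of study drug or completion of study drug".
- **Which data are blinded-phase.** The cutoff is the first open-label dose date, and for treated open-label entrants "data collected up to the cutoff date will be considered as DB phase data". HIV tests are not among the data types for which the cutoff date itself is moved to the open-label phase.
- **When the at-risk period ends.** For uninfected participants, SAP 6.2.3 uses "the date of the last post-baseline HIV laboratory test (either local HIV or Covance HIV laboratory tests) during the DB phase".
- **What happens at the exit visit.** Protocol 6.4 schedules rapid and central HIV tests and covers two cases. Participants who have already taken that day's blinded dose are told that "they should not begin dosing with OL F/TAF until the next day". The other case begins "If the participant has not taken a dose of blinded study drug on the day of the visit", and then "they should take their first dose of OL F/TAF on the same day of the end of blinded treatment phase visit".

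**The concern.** A percentage labelled as PEP use while off study drug will be read as describing people who stopped prophylaxis and stayed under HIV follow-up. Someone who takes a blinded tablet one day and an open-label tablet the next has not stopped. If such people are in the denominator, they contribute about one day each in which PEP could be counted, and they lower the percentage without telling the reader anything about off-drug behaviour.

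The entry rule is also arbitrary. Two completers with identical daily dosing are classified differently because one takes the tablet before the clinic visit and the other after it.

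The SAP is not uniform here either. The on-treatment efficacy sensitivity analysis in SAP 6.2.6 calls time off-treatment only after more than 10 days (F/TDF) or 16 days (F/TAF) since stopping, and it ends follow-up at the first open-label dose. SAP 7.6.4 does neither.

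**Working it through.** The plan states no count or percentage for off-treatment PEP use, so there is no figure to reproduce. The check has two parts: apply the date rules, then see how the result depends on quantities that the documents do not give.

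**Date rules.** Let the exit visit and its HIV test fall on day *v*. I read the unqualified last dose date in 7.6.4 as the blinded-phase one, in line with SAP Appendix 12, item 14.

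| | Blinded dose already taken on day *v* | Not yet taken on day *v* |
|---|---|---|
| Last blinded dose | *v* | *v* − 1 |
| First open-label dose | *v* + 1 | *v* |
| Test counts as blinded-phase data | yes (*v* is before the cutoff) | yes (*v* is the cutoff) |
| At-risk end minus last dose | 0 days | 1 day |
| Interval from blinded to open-label dose | 1 day | 1 day |
| In off-treatment denominator | no | **yes** |

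Both participants dosed on consecutive days. Only the second is counted as off treatment.

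Completers who decline the open-label phase are different. Protocol 6.4 brings them back for a 30-Day Follow-Up visit, so they have real off-drug time and belong in the denominator.

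**Size.** Let *M* be the direct rollovers with a one-day gap and *D* the other participants in the denominator. If the rollovers contribute no PEP use, the reported percentage is *D*/(*D* + *M*) times the undiluted one.

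The only documentary input is *N* = 5387, the Safety Analysis Set in SAP Appendix 3, which is an upper bound for the FAS. Everything else is assumed: *c* is the share completing, *e* the share of completers entering the open-label phase, *u* the share of entrants not dosed before the exit visit, and *h* the share of premature stoppers with a later HIV test. I also assume that 90% of completers who decline the open-label phase attend follow-up.

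- *M* = *N* × *c* × *e* × *u*
- *D* = *N* × (1 − *c*) × *h* + *N* × *c* × (1 − *e*) × 0.9

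With *c* = 0.80, *e* = 0.90 and *h* = 0.70, *D* = 5387 × 0.20 × 0.70 + 5387 × 0.80 × 0.10 × 0.9 = 754 + 388 = 1142. An undiluted 5% would then be reported as follows:

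| *u* | *M* | Reported for a true 5% |
|---|---|---|
| 0 | 0 | 5.0% |
| 0.05 | 194 | 4.3% |
| 0.10 | 388 | 3.7% |
| 0.25 | 970 | 2.7% |
| 0.50 | 1939 | 1.9% |
| 0.75 | 2909 | 1.4% |

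The wider grid takes *c* from 0.70 to 0.85, *e* from 0.80 to 0.95, *u* from 0.10 to 0.75 and *h* from 0.50 to 0.90. Its extremes are:

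- Most dilution (*c* 0.85, *e* 0.95, *u* 0.75, *h* 0.50): 610/(610 + 3263) = 0.16.
- Least dilution (*c* 0.70, *e* 0.80, *u* 0.10, *h* 0.90): 2133/(2133 + 302) = 0.88.

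As *u* goes to zero the factor goes to 1.

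**The case against.** The strongest objection is that the last dose date comes from the eCRF, not from the hour at which a tablet was taken. Under SAP 3.8.1, if a site enters the exit-visit date as the last blinded dose, the gap is 0 days and the participant drops out. A completely missing date is imputed as the latest drug, clinic or laboratory date excluding the 30-day follow-up, which gives the same result when the exit visit is latest. This stands as a limit on numbers: fewer people may be affected than dosing habits alone suggest. It does not remove the problem, because a correctly recorded previous-day dose still admits the participant. The same section also moves a last blinded dose recorded after the first open-label dose back to the day before that dose, which can itself create the one-day gap.

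A second objection is that the added participants need not have zero PEP use. A course that spans the exit visit, is marked as ongoing or has partial dates can be counted as off-treatment. This also stands, so the percentage will generally be lowered rather than always.

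Third, 7.6.4 attaches no test or decision to this summary, and the number of participants using PEP and the uses per participant do not depend on the denominator. That is correct and sets the importance of the point.

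A reader might infer that rollovers swamp the denominator and that the percentage will be several times too low. The documents do not support that: they give no completion, open-label entry or dosing-time figures, and the range above includes mild dilution.

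**Conclusion.** The rule is wrong as written. By the SAP's own definitions, direct rollovers whose last blinded dose is recorded as the day before the exit visit enter the off-treatment PEP denominator with essentially no off-drug time, while otherwise identical completers recorded as dosed on the visit day do not.

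The size is not documented. Under the assumed grid the reported percentage is about 0.16 to 0.88 times the undiluted one, and dilution vanishes if nearly all open-label entrants had dosed before the visit. Those figures rest on assumed shares for completion, open-label entry, dosing before the visit and later testing, and on no PEP use among the rollovers.

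It would be wrong to infer that every completer is miscounted. Those dosed on the visit day are excluded, and those who decline the open-label phase have about 30 days off drug. Nor does the point reach the HIV results: the endpoint, margin, alpha and power are untouched, and SAP 6.2.6 has its own rules for off-treatment time. Nothing in the documents suggests that the artefact differs by arm. It is a minor point about one descriptive percentage.

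**What to change.** For both the off-treatment PEP numerator and its denominator, end the off-treatment window at the earlier of the at-risk end date and the day before the first open-label dose. Include only participants whose window ends after the last blinded dose. In the problem case the window then ends on *v* − 1, which is the last dose date, so direct rollovers leave. Someone who interrupted blinded drug well before open-label entry keeps a positive window and stays; excluding everyone with an open-label dose would lose that person.

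Also report PEP uses per 100 off-treatment person-years over the same window. Premature stoppers whose only later HIV test is at the ESDD visit, due within 72 hours of stopping (Protocol 6.7.1), remain in the percentage with at most a few days each. In a person-time rate they carry little weight. State in 7.6.4 that the last dose date is the blinded-phase one, and note that off-treatment there differs from the 10- and 16-day definition in 6.2.6.

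The cost is one added date condition and one person-time calculation in the SAP and program, using dates already collected.

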### 7.6.5. Concomitant Non-ARV Medications

Concomitant non-ARV medications (ie, medications other than study drug that are taken while receiving study drug) will be coded using the WHO Drug Dictionary. The WHO preferred name and drug code will be attached to the clinical database. Use of concomitant medications from Study Day 1 up to the date of the DB phase last dose of study drug will be summarized (number and percentage of subjects) by treatment group and preferred name. Multiple drug use (by preferred name) will be counted only once per subject. The summary will be sorted by decreasing total frequency. For drugs with the same frequency, sorting will be done alphabetically.

If the start or stop date of non-ARV medications is incomplete, the month and year (or year alone, if month is not recorded) of the start or stop date will be used to determine whether the non-ARVs are concomitant or not. The medication is concomitant if the month and year of the start or stop (or year of the start or stop, if month is not recorded) of the medication does not meet either of the following criteria:

- The month and year of start of the medication is after the date of the DB phase last dose of study drug
- The month and year of stop of the medication is before the date of the first dose of study drug

If the start and stop date of non-ARV medications are complete, the start date is not after the DB phase last dose date and the stop date is not before first dose date, or the non-ARV medications are marked as ongoing and start date is on or before the DB phase last dose date, the non-ARV medications are concomitant for the DB phase of the study. Medications with completely missing start and stop dates will be included in the concomitant medication non-ARV summary, unless otherwise specified.

Summaries of non-ARV concomitant medications will be provided for the Safety Analysis Set. Subjects with any non-ARV concomitant medications will be listed. No inferential statistics will be provided.

### 7.7. Other Safety Measures

Physical examination data was not collected in the eCRF. Therefore, it will not be included in the analysis.

### 7.8. Changes From Protocol-Specified Safety Analyses

The criterion for a nonmissing postbaseline BMD value is not required for either the Hip or Spine DXA Analysis Sets. As the BMD sensitivity analyses using the BlOCF imputation method do not require subjects to have at least 1 postbaseline value this condition is removed from the Hip and Spine DXA Analysis Sets used for all BMD analyses.

### 8. PHARMACOKINETIC ANALYSES

The PK analysis was already performed in the primary analysis and will not be repeated in this analysis.

### 9. SEXUAL RISK BEHAVIOR

Sexual risk characteristics including outcomes of high-risk sexual behavior (sexually transmitted infections [STI]) while at risk of HIV infection during the DB phase of the study will be summarized for the subjects in the FAS.

All sexual risk characteristics data will be included in data listings.

## 9.1. Sexually Transmitted Infections While At Risk of HIV Infection During the DB phase

STIs considered to have occurred while at risk of HIV infection are defined as those occurring after the first dose date (excluding the Day 1 first dose date) and on or before the end date (end date Day 1 date +1) where end date is defined as the last at risk of HIV infection date during the DB phase defined in Section 6.2.3.

### 9.2. Sexually Transmitted Infections

## 9.2.1. Definition of STI Infections from Laboratory Data While At Risk of HIV Infection During the DB phase

9.2.1.1. Definition of Chlamydia or Gonorrhea Infection by Anatomic Location (Rectal, Pharyngeal, or Urethral) from Laboratory Data

Subjects with chlamydia or gonorrhea infection at each anatomic location are defined as subjects with results of either 'detected' from the urine Covance central laboratory tests or 'positive' from the rectal or pharyngeal local laboratory tests captured on the Local Lab eCRFs for chlamydia or gonorrhea.

For each STI (chlamydia or gonorrhea) and anatomic location (rectal, pharyngeal, or urethral) separately, the number of unique infection events is defined based on unique laboratory collection dates within each subject; however, within a subject, multiple positive infection results from laboratory collection dates within a 14 day period will be counted as only one infection event on the date of the first positive result.

### 9.2.1.2. Definition of Syphilis Infection (Investigator Reported)

Subjects with syphilis infection are defined as subjects with a diagnosis of either new, re-infection or missing syphilis infection status (excluding treatment failures) from the Syphilis Diagnosis eCRF.

The number of unique syphilis infection events is defined based on unique diagnosis dates within each subject for each disease stage and disease status as captured on the Syphilis Diagnosis eCRF with a syphilis infection status of new, re-infection or missing (excluding treatment failures).

#### 9.2.2. Summaries of Gonorrhea, Chlamydia or Syphilis STIs While At Risk of HIV Infection During the DB phase

The following summaries of STIs while at risk of HIV infection will be provided by treatment group for the FAS:

5 · `	The title is a second of the s
•	Gonorrhea or Chlamydia (based on laboratory data)
	Rectal
	Pharyngeal
	Urethral (Urine)
•	Gonorrhea (based on laboratory data)
	Rectal
	Pharyngeal
	Urethral (Urine)
•	Chlamydia (based on laboratory data)
	Rectal
	Pharyngeal
	Urethral (Urine)
•	Syphilis (based on investigator report)
	Disease stage (Primary, Early Latent, Secondary, Tertiary, Late Latent, Other or Missing)
	Status (New, Re-infection or Missing)
	r each STI summary above, the number and percentage of subjects will be summarized by atment group and overall on the FAS.

For each STI summary above, the STI incidence rate per 100 person-years of follow-up will be computed as the number of unique events occurring while at risk of HIV infection divided by the summation of all subjects' total number of years (where a year is 365.25 days) of follow-up while at risk of HIV infection (defined in Section 9.1.) The STI incidence rates will be summarized by treatment group and overall for the FAS.

